#### **7.11. Other Safety Measures**

Neuropsychiatric assessment will be based on the psychosocial health summary and domains of the PedsQL™ SF 15.

A data listing will be provided for subjects who become pregnant during the study.

#### **7.12. Changes From Protocol-Specified Safety Analyses**

There are no deviations from the protocol-specified safety analyses.

## **8. PHARMACOKINETIC ANALYSES**

### **8.1. PK Analysis in the PK Lead-in Phase (Intensive PK Analysis)**

Intensive PK Analysis will be performed using the Lead-in Phase PK Analysis Set. Concentrations of SOF, GS-331007, GS-566500 and VEL from subjects in the PK lead-in Phase over sampling time will be listed and summarized for each age cohort using descriptive statistics (n, arithmetic mean, geometric mean and its 95% confidence interval, coefficient of variation [%CV], SD, median, Q1, Q3, minimum, and maximum) by nominal time. For Cohort 1 and 2, plasma samples will be collected for PK analyses following dosing of study drugs on Day 7 at the following time points: 0 (predose), 0.5, 1, 2, 3, 4, 6, 8, and 12 hours postdose. For Cohort 3, plasma samples for PK analyses will be collected at the following time points: 0 (predose), 0.5, 1, 2, 3, 4, 8, and 12 hours postdose. PK parameters from subjects in the PK lead-in Phase for each age cohort will be summarized (e.g;  $AUC_{\tau}$ ,  $AUC_{last}$ ,  $C_{max}$ ,  $T_{max}$ ,  $C_{last}$ ,  $T_{last}$ ,  $C_{\tau}$ ,  $T_{1/2}$ , volume of distribution and clearance [CL/F], as appropriate).

SOF, GS-331007 and VEL exposures ( $AUC_{\tau}$ ,  $C_{max}$ , and  $C_{\tau}$ , if applicable) in each age cohort will be compared with SOF/VEL adult populations. The primary endpoint of this analysis will be evaluated by carrying out an analysis of variance (ANOVA) for log-transformed SOF, GS-331007 and VEL  $AUC_{\tau}$ . The secondary endpoints of this analysis will be the  $C_{max}$  of SOF, VEL and GS-331007 and  $C_{\tau}$  of VEL. The 90% confidence intervals will be constructed for the ratio of geometric means of each PK parameters.

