Selection of doses of SOF/VEL FDC for adolescents and younger age groups will target systemic exposures similar to those observed in adults at the proposed marketed dose, and will take into account body weight/body surface area, the potential ontogenic changes in transporters and metabolic enzymes that govern the disposition of SOF and VEL, and the results obtained in older age groups. Available data suggest comparable hepatic expression of CYP2B6 and CES1 in adolescents and adults with modestly decreased expression in children, and comparable levels of CYP2C8 and CYP3A4 to adults from a young age (~3-6 years of age) {[Johnson 2006](#)}; however, little is known about the developmental regulation of Pgp, CES, and CatA.

In this current study, the adult clinical dose of SOF/VEL FDC 400/100 mg is being evaluated in adolescents (12 to <18 years old), while a lower dose SOF/VEL FDC 200/50 mg is being evaluated in children (6 to <12 years old). As described in Section 1.2.2.3, the appropriateness of these doses is supported by data from the Cohort 1 and Cohort 2 PK Lead-in subjects, respectively, which demonstrated SOF, GS-331007 and VEL exposure to be within the range of adult exposures associated with safety and efficacy in the Phase 2/3 SOF/VEL adult population ([Table 1-1](#) and [Table 1-2](#)).

In Cohort 3 (3 to <6 years old), a dose of SOF/VEL FDC 200/50 mg is proposed for evaluation in children weighing ≥ 17 kg, whereas a dose of SOF/VEL FDC 150/37.5 mg is proposed for evaluation in children weighing < 17 kg. These proposed doses are supported by scaling of adult exposures based on correlations between body weight and clearance capacity (liver volume/size for VEL and SOF, and renal capacity for GS-331007) for the expected body weight range in children (3 to < 6 years of age) as demonstrated in [Figure 1-1](#). Based on this scaling approach, these doses of SOF/VEL FDC are expected to achieve mean systemic exposures of SOF, GS-331007, and VEL within the range of those observed in the Phase 2/3 adult population. Safety and PK data in children who enroll in the PK Lead-in Cohort 3 will be evaluated to confirm the appropriateness of the dose for this age group.

Figure 1-1. Predicted SOF, GS-331007 and VEL AUC_{tau} following administration of SOF/VEL FDC 200/50 mg or 150/37.5 mg to Children 3 to <6 years of age who are ≥ 17 kg or < 17 kg, respectively

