3.3. Study Treatments

3.3.1. PK Lead-in Phase

The PK Lead-in Phase will evaluate and/or confirm the age appropriate SOF/VEL FDC dose by analyzing PK, safety, and antiviral activity of SOF/VEL FDC through 7 days of dosing for each cohort. Three cohorts of at least 17 subjects each will be sequentially enrolled:

- Cohort 1: 12 to < 18 years old
- Cohort 2: 6 to < 12 years old
- Cohort 3: 3 to < 6 years old
 - At least 6 subjects weighing \geq 17 kg
 - At least 6 subjects weighing < 17 kg

[figure not shown]
The study will start with Cohort 1. Subjects will receive a SOF/VEL FDC 400/100 mg adult tablet or 2 x 200/50 mg tablets (if determined necessary based on SOF/VEL swallowability assessment) once a day for 7 days with intensive PK conducted on Day 7. If unable to swallow the tablet formulations, the subjects will receive SOF/VEL FDC 400/100 mg oral granules (8 x 50/12.5 mg packets).

Cohort 2: Subjects will receive SOF/VEL FDC 200/50 mg tablets once daily. If unable to swallow the tablet formulations, the subjects will receive SOF/VEL FDC 200/50 mg oral granules (4 x 50/12.5 mg packets).

Cohort 3: Subjects will receive SOF/VEL FDC 200/50 mg oral granules (4 x 50/12.5 mg packets) once daily for subjects weighing \geq 17 kg. SOF/VEL FDC 150/37.5 mg oral granules (3 x 50/12.5 mg packets) will be administered once daily for subjects weighing < 17 kg.

Figure 3-1. PK Lead-in Phase Study Schema

PK Lead-in

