8.6. Pharmacokinetic Analysis

PK analysis will be performed for PK Lead-in using the intensive PK Lead-in analysis set. The concentration data of VEL, SOF and metabolites (GS-566500 and GS-331007) over sampling time will be listed and summarized by nominal time and cohort. Pharmacokinetic parameters (e.g., AUC_{τ} , C_{\max} , T_{\max} , C_{last} , T_{last} , C_{τ} , and $t_{1/2}$) will be listed and summarized by cohort using descriptive statistics (eg, sample size, arithmetic mean, geometric mean, % coefficient of variation, standard deviation, median, minimum, and maximum). Plasma concentrations of the analytes over time will be plotted in semi logarithmic and linear formats as mean \pm standard deviation.

To evaluate if the exposures of SOF, GS-331007 and VEL achieved in pediatric subjects of this study are similar to the exposures observed in adult subjects, SOF, GS-331007 and VEL exposure data from this study will be compared to the integrated adult data. The primary endpoint of this analysis will be evaluated by carrying out an analysis of variance (ANOVA) for log-transformed SOF, GS-331007 and VEL AUC_{τ} . The secondary endpoints of this analysis will be the C_{\max} of SOF, VEL and GS-331007 and C_{τ} of VEL. The 90% confidence intervals will be constructed for the ratio of geometric means of each PK parameters. The equivalence boundary is set as 70% to 200%.

Dose ranging studies for SOF established that a dose of 200 mg results in suboptimal exposure compared to the 400 mg dose, and no clinically significant exposure-safety relationships were observed across a broad range of GS-331007 exposure. The Phase 1 dose ranging study GS-US-281-0102 established the anti-HCV activity of VEL and the E_{\max} models indicated that subjects will experience near maximal antiviral response (99.5% of E_{\max}) at a VEL dose of 100 mg. In the Phase 2/3 population treated with SOF/VEL FDC 400/100 mg, virologic response rates were high across all HCV genotypes and quartiles of exposure for VEL, SOF and GS-331007, including for subjects with cirrhosis, with no consistent trends in exposure-efficacy or exposure-safety relationships. Given the observed safety and efficacy profile and the lack of exposure-response across all quartiles of SOF/VEL exposure, the bounds of 70-200% support identification of a clinically relevant difference in SOF, GS-331007 or VEL exposure in the pediatric population.

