In all pediatric age groups, the targeted exposures for SOF, GS-331007 and VEL are the adult equivalent for which safety and efficacy has been established. Assuming similar variability for SOF, GS-331007 or VEL AUC_{τ} in the pediatric population compared to adults, the predicted 90% CIs of the geometric mean ratio (GMR) will be contained within the bounds of 70% to 200%.

In the event more than one subject in each cohort exhibits VEL, SOF, or GS-331007 AUC_{tau} exposures less than the 2.5th percentile of adult values, a dose adjustment may be required for the cohort as appropriate.

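### Cohort 3 tests two doses split at 17 kg, but the planned PK summaries and adult ratios are by age cohort only, so no planned ratio checks either dose

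*SAP*

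**What the plan says.** Protocol 3.3.1 and SAP 1.2.1 enrol at least 17 children aged 3 to <6 years in Cohort 3. Those weighing 17 kg or more receive 200/50 mg and the lighter children 150/37.5 mg. Each band has a minimum size, for example "At least 6 subjects weighing < 17 kg". Protocol 1.3 states that the two doses are "supported by scaling of adult exposures based on correlations between body weight and clearance capacity", and Figure 1-1 predicts AUCtau for each dose in its own weight band.

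The PK analysis does not carry the split. SAP 8.1 says that PK parameters "for each age cohort will be summarized" and that exposures "in each age cohort will be compared with SOF/VEL adult populations". Protocol 8.6 says that parameters "will be listed and summarized by cohort using descriptive statistics" and names no grouping for its adult comparison (ANOVA on log AUCtau, 90% CI for the geometric mean ratio, bounds 70% to 200%). Its low-exposure rule is also counted per cohort: if more than one child falls under the adult 2.5th percentile, "a dose adjustment may be required for the cohort as appropriate".

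The SAP does separate these children elsewhere: prescribed amount by weight band in 4.2.2, and palatability by dose in 7.10, where 150/37.5 mg has its own category.

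**The concern.** The primary objective of the lead-in is to evaluate steady-state PK and confirm the dose, with AUCtau as the primary endpoint. Ages 3 to <6 have two doses to confirm, but the plan specifies one ratio per analyte, averaged over both in proportion to how many children fall in each band. That average stands for each dose only if both bands reach similar exposure. Protocol 1.3 itself notes that "little is known about the developmental regulation of Pgp, CES, and CatA", so similar exposure is an assumption to be tested.

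Off-target exposure in one band can be partly offset by the other. This is more likely to pass unseen on the high side, because the low-exposure rule has no upper counterpart.

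**Working it through.** **Inputs.** Cohort size is 17 (the minimum), so the lighter/heavier split can run from 6/11 to 11/6. The dose ratio, lighter to heavier, is 150/200 = 0.75. The bounds are 0.70 to 2.00 with a 90% CI. There were 1425 adults for VEL (982 for SOF), from the footnote to the preliminary Cohort 2 PK table (protocol 1.2.2.3). No AUCtau CV is visible in the available text, so the adult Cmax CV in that table (53.9%, analyte label not visible) serves as a stand-in: log SD = sqrt(ln(1 + 0.539²)) = 0.505.

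**The plan's own figures.** The table gives a Cmax ratio of 215 (172, 268) with 17 children. The interval is ratio × exp(± t × SD × sqrt(1/17 + 1/1425)), with t = 1.646. An SD of 0.505 gives 175.5 to 263.3. The published limits imply SD = [ln(268/172)/2] / (1.646 × 0.244) = 0.552. I therefore show SD 0.40 to 0.55. The statement in protocol 8.6 that the predicted CIs fall within 70% to 200% cannot be reproduced without an AUCtau CV. It is plausible for a whole cohort: 17 children at a true ratio of 100% and SD 0.505 give 81.6% to 122.5%.

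**What pooling does.** With n lighter children of 17, pooled ratio = (lighter ratio)^(n/17) × (heavier ratio)^((17−n)/17).

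*Equal exposure in both bands:* no distortion.

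*Clearance unrelated to weight:* the lighter band's AUC is 0.75 of the heavier band's. Lighter/pooled = 0.75^((17−n)/17) and heavier/pooled = 0.75^(−n/17).

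| Lighter/heavier | lighter/pooled | pooled overstates lighter by | heavier/pooled | pooled understates heavier by |
|---|---|---|---|---|
| 6/11 | 0.830 | 20% | 1.107 | 10% |
| 8/9 | 0.859 | 16% | 1.145 | 13% |
| 11/6 | 0.903 | 11% | 1.205 | 17% |

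**How often the pooled CI stays inside 70-200%.** Each case has 100,000 simulated trials with one analyte, SD 0.505, ANOVA pooled variance and a 90% t-interval. The second figure also requires that the low-exposure rule stays silent (at most one child below −1.96 SD on the log scale). The off-target band is listed first.

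| True ratios | split 6/11 | split 8/9 | split 11/6 |
|---|---|---|---|
| 0.65 / 0.867 (the 0.75 relation) | 23%; 20% | 16%; 14% | 8%; 7% |
| 0.60 / 1.10 (assumed) | 61%; 48% | 38%; 29% | 12%; 9% |
| 2.2 / 1.0 (assumed) | 96%; 93% | 83%; 81% | 43%; 43% |

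Over SD 0.40 to 0.55, the first figure for 0.60/1.10 runs 79% to 55%, 53% to 34% and 15% to 11%. For 2.2/1.0 it runs over 99% to 92%, 95% to 77% and 59% to 39%.

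The last two rows are stress cases. If the lighter band is the low one, 0.60/1.10 needs lighter children to have (0.75/0.60)/(1/1.10) = 1.375 times the CL/F of heavier ones. The 2.2/1.0 case needs 0.34 times if the lighter band is high, or 1.65 times if the heavier band is high.

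Suppose all three analytes share the pattern, all must pass and no more than one child may be low on any analyte. With within-child correlation 0 to 0.8, the figures become 6-25%, 1-12% and at most 3% for 0.60/1.10, and 70-82%, 48-66% and 7-26% for 2.2/1.0.

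**One worked case.** Six children at 60% and 11 at 110% pool to exp[(6 ln 60 + 11 ln 110)/17] = 88.8%, 90% CI 72.5% to 108.8%, inside the bounds. The six alone give 42.7% to 84.3%, with estimate and lower limit both below 70%.

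**The case against.** The case against accepts the wording and disputes its consequence.

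- **The dose review is not tied to the SAP 8.1 ratio.** It happens before further children of that age enrol, while the SAP's own planned analyses are the DMC reviews and a final analysis after posttreatment Week 24. Protocol 8.6 lists individual parameters, and with about 17 children whose dose follows from weight a reviewer can read exposure by band. This stands as a practical safeguard, but no document plans that reading or gives it a ratio.
- **Dose effects are already to be explored, according to the protocol synopsis.** They are, but without a method, and SAP 8.1 does not take the point up.
- **Population PK is planned.** SAP 8.2 combines lead-in and Treatment Phase samples, reports separately and names no weight-band output.
- **Both bands target adult exposure, so pooling assesses the age group's weight-tiered regimen.** That is fair if the scaling holds.
- **The low-side risk is limited.** Under the 0.75 relation with the lighter band at 0.65, the pooled CI falls outside the bounds in 77% to 92% of trials. Substantial masking needs the assumed ratios.
- **The bounds are not a strict gate.** SAP 8.1 does not repeat them, and the 215 (172, 268) result did not prevent that dose from being considered appropriate. In adults on 400/100 mg protocol 8.6 reports "no consistent trends in exposure-efficacy or exposure-safety relationships", which softens the high-side worry.
- **Earlier practice respected dose.** In Cohort 2, 3 of 20 children who received another dose were left out of the PK analysis. No such rule is written for Cohort 3, so the precedent favours separating the doses.

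**Conclusion.** The concern holds and should be fixed. Neither document plans a PK summary or an adult ratio for either Cohort 3 dose, in a phase whose primary purpose is to confirm the dose. That conclusion rests on the text alone.

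The size depends on how far the weight scaling fails: nil if it holds, 10% to 20% distortion if clearance does not fall with weight, and more only under ratios harsher than the protocol predicts. The pass rates rest on a Cmax-based log SD, 17 children and assumed true ratios. They show that masking can happen and do not say that it is likely. Nothing here bears on which dose is right.

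**What to change.** In SAP 8.1 and protocol 8.6, report the following for Cohort 3 by weight band and dose (17 kg or more, 200/50 mg; under 17 kg, 150/37.5 mg), beside the pooled cohort figure:

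- concentration and PK parameter summaries;
- geometric mean ratios to adults with 90% CI, from the same ANOVA with the two bands and adults as levels;
- the number of children below the adult 2.5th percentile.

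Label these as descriptive, with no new pass/fail criterion and no change to any dose or to the dose-adjustment rule. This would also give the synopsis's promised look at dose effects a method.

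The cost is two extra columns in existing tables and no new data. The drawback is precision. At n = 6 the CI extends by a factor of exp(t × SD × sqrt(1/6 + 1/1425)) each side: 1.31, 1.41 or 1.45 for SD 0.40, 0.505 or 0.55. A band truly at 1.0 would lie inside 70-200% in only about 70%, 49% or 40% of trials, against 89% for 17 children at SD 0.505. The by-band figures can describe each dose but cannot formally confirm it, and the text should say so.

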### **8.2. Population PK Analysis**

Population PK modeling will be applied on the combined data from both PK samples collected in PK Lead-in Phase and PK samples collected in the Treatment Phase to characterize the PK of SOF, GS-331007 and VEL using mixed-effect modeling techniques. Estimated PK parameters using the population PK model will be presented in a separate Population PK report.

## **10. SOFTWARE**

SAS® Software Version 9.4. SAS Institute Inc., Cary, NC, USA.

## 11. SAP REVISION

Revision Date (DD MMM YYYY)	Section	Summary of Revision	Reason for Revision

## 12. APPENDICES

- Appendix 1. Study Procedures Table
- Appendix 2. Tanner Stages\*
- Appendix 3. PedsQL™ Score Calculation Algorithms

**Appendix 1. Study Procedures Table**

**Appendix Table 1. PK Lead-in Phase: Screening and On-Treatment Study Visits**

	Screening (-28 days)	On-treatment		
		Day 1 i	Day 3 Telephone call	Day 7 (+ 3 days)
Clinical Assessments				
Informed Consent / Assent	X			
Determine Eligibility	X	X		
Medical History	X			
Parental Height	X a	X a		
Complete Physical Examination	X	X		
Symptom-directed Physical Examination				X
Tanner Pubertal Stage Assessment b		X		
Vital Signs c	X	X		X
Body Weight and Height d	X	X		X
Bone Age Assessment		X		
AEs and Concomitant Medications	X	X	X	X
Transient Elastography, if available	X c	X c		
Pregnancy Prevention Counseling f		X		
SOF/VEL Swallowability Assessment	X g	X g		
SOF/VEL Acceptability Questionnaires		X		
Quality of Life Survey		X h		
Review of Study Medication Compliance				X
Study Drug Dispensing i		X		
Subject Dosing Diary j		X	X	X
Laboratory Assessments				
Hematology, Chemistry, Coagulation	X	X		X
HbA1c, Fibrotest ® , APRI	X			
TSH	X			
Alpha-1 anti-trypsin	X			

	Screening (-28 days)	On-treatment		
		Day 1 i	Day 3 Telephone call	Day 7 (+ 3 days)
HIV testing, HCV antibody, HBsAg, HBsAb, HbCAb, and HAV antibody	X			
HBV DNA k	X			
HCV RNA	X	X		X
HCV Genotyping	X			
Viral Sequencing l		X		X
Serum or Urine Pregnancy Testing m	X	X		X
IL28B Genotyping		X		
Urinalysis	X	X		X
Urine Drug Screen	X			
CCI				
Intensive PK				X o

- a Biological parental height, if not collected at Day 1.
- b If the assessment determines that the subject is at a Tanner 5 at Day 1, no further Tanner Pubertal Stage Assessments are to be completed.
- c Vital signs include blood pressure, pulse, respiratory rate and temperature.
- d Height should be without shoes and should be collected by the same personnel, if possible.
- e May be performed at Screening up to Day 1.
- f Including partner pregnancy prevention for male participants (all subjects  $\geq$  12 years old and subjects < 12 years old at the discretion of the investigator based on subject's pubertal status).
- g Swallowability can occur at Day 1 if not completed during screening.
- h Quality of life survey will be completed by all subjects and their parent/legal guardian. Subject and parent/legal guardian is to review questionnaire and write/mark answers directly onto the questionnaire.
- i Day 1 assessments must be performed prior to dosing. The IWRS system will provide direction on the specifics of each subject's study drug dispensing.
- j **CCI**
- k HBV DNA testing done only when subjects are HbCAb positive at Screening.
- l Plasma samples will be collected and stored for potential HCV sequencing and other virology studies.
- m Females of childbearing potential only. Serum pregnancy test performed at screening and for confirmation of positive urine pregnancy test.
- n For subjects who provide consent, a blood sample should be drawn at the Day 1 visit. If not obtained at this visit, the sample may be drawn at any time during the study.
- o **Cohorts 1 and 2**, plasma samples will be collected for PK analyses following dosing of study drug on Day 7 at the following time points: 0 (predose), 0.5, 1, 2, 3, 4, 6, 8, and 12 hours postdose. **Cohort 3**, plasma samples for PK analyses will be collected at the following time points: 0 (predose), 0.5, 1, 2, 3, 4, 8, and 12 hours postdose. Subjects should come in a fasted state for the Week 4 or Week 8 intensive PK visit (i.e., no food or drink except water at least 8 hours prior to the Week 4 or Week 8 intensive PK visit). Subjects and/or parents/legal guardians should also be instructed that the Week 4 or Week 8 dose of SOF/VEL FDC must not be taken prior to the visit and until the evaluations listed below are completed.

**Appendix Table 2. Treatment Phase: Screening and On-Treatment Study Visits**

	Screening i,k (-28 days)	Day 1 k	Week 1 k	Week 4	Week 8	Week 12	Early Termination
Clinical Assessments							
Informed Consent / Assent	X						
Determine Eligibility	X	X					
Medical History	X						
Parental Height	X a	X a					
Complete Physical Examination	X	X				X	X
Symptom-Directed Physical Examination			X	X	X		
Tanner Pubertal Stage Assessment b		X				X	X
Vital Signs c	X	X	X	X	X	X	X
Body Weight and Height d	X	X	X	X	X	X	X
Bone Age Assessment		X					
AEs and Concomitant Medications	X	X	X	X	X	X	X
Transient Elastography, (if available)	X c	X c					
Pregnancy Prevention Counseling f		X				X	X
SOF/VEL Swallowability Assessment	X g	X g					
SOF/VEL Acceptability Questionnaire h		X				X	X
Quality of Life Survey i		X				X	X
Review of Study Medication Compliance				X	X	X	X
Study Drug Dispensing j		X		X	X		
Subject Dosing Diary l		X	X	X	X	X	
Laboratory Assessments							
Hematology, Chemistry, Coagulation	X	X	X	X	X	X	X
HbA1c, Fibrotest ® , APRI	X						
TSH	X					X	X
Alpha-1 anti-trypsin	X						
HIV testing, HCV Antibody, HBsAg, HBsAb, HBcAb, HAV Antibody	X						
HBV DNA m	X			X	X	X	X
HCV RNA	X	X	X	X	X	X	X
HCV Genotyping	X						

	Screening i,k (-28 days)	Day 1 k	Week 1 k	Week 4	Week 8	Week 12	Early Termination
Viral Sequencing n		X	X	X	X	X	X
Serum or Urine Pregnancy Testing o	X	X		X	X	X	X
IL28B Genotyping		X					
Urinalysis	X	X					
Urine Drug Test	X						
CCI							
Single PK			X			X	X
Two sparse PK Samples collected predose and between 15 minutes and up to 4 hours postdose q				X	X		

**CCI**

- a Biological parental height, if not collected at Day 1.
- b If the assessment determines that the subject is at a Tanner 5 at Day 1, no further Tanner Pubertal Stage Assessments are to be completed.
- c Vital signs include blood pressure, pulse, respiratory rate, and temperature.
- d Height should be without shoes and should be collected by the same personnel, if possible.
- e May be performed at Screening up to Day 1.
- f Including partner pregnancy prevention for male participants (all subjects ≥ 12 years old and subjects < 12 years old at the discretion of the investigator based on subject's pubertal status).
- g Swallowability can occur at Day 1 if not completed during screening.
- h A questionnaire will be administered to subjects to assess acceptability and palatability of the formulation they received on Day 1, Week 12, and Early Termination (as applicable). If the subject is unable to complete the questionnaires, the parent/legal guardian will complete the questionnaire on their behalf. The subjects' parent/legal guardian will also complete a questionnaire on Week 12 or Early Termination (as applicable) for their assessment of acceptability of the formulation the subject received.
- i Quality of life survey will be completed by all subjects and their parent/legal guardian. Subject and parent/legal guardian is to review questionnaire and write/mark answers directly onto the questionnaire.
- j Day 1 assessments must be performed prior to dosing. The IWRS system will provide direction on the specifics of each subject's study drug dispensing.
- k Subjects rolling over from PK Lead in will not be required to repeat screening, Day 1 or Week 1 visits in the Treatment Phase.
- l **CCI**
- m HBV DNA testing done only when subjects are HBcAb positive at Screening.
- n Plasma samples will be collected and stored for potential HCV sequencing and other virology studies.
- o Females of childbearing potential only. Serum pregnancy test performed at screening and for confirmation of positive urine pregnancy test.
- p For subjects who provide consent, a blood sample should be drawn at the Day 1 visit. If not obtained at this visit, the sample may be drawn at any time during the study.

q **CCI**

r **CCI**

